3.1.1. Investigational Drug

3.1.1.1. Supplier(s)

Celgene Corporation will supply POMALYST® (CC-4047) to study participants at no charge through Celgene's Pomalidomide Risk Evaluation and Mitigation Strategy (POMALYST REMSTM).

3.1.1.2. Dosage form

CC-4047 will be supplied as 0.5mg capsules for oral administration.

3.1.1.3. Packaging

CC-4407 will be shipped directly to the pharmacy at the study site. Bottles will contain a sufficient number of capsules for one cycle of dosing.

3.1.1.4. Labeling

CC-4047 investigational supplies are dispensed in individual bottles of capsules. Each bottle will identify the contents as study medication. In addition, the label will bear Celgene's name, quantity contained and the standard caution statement as follows: Caution: New drug - Limited by Federal law to investigational use. The study drug label must be clearly visible. Additional labels must not cover the Celgene label.

CC-4047 should not be handled by FCBP unless wearing gloves.

3.1.1.5. Receipt of study drug

The Investigator or designee is responsible for taking an inventory of each shipment of study drug received, and comparing it with the accompanying study drug accountability form. The Investigator will verify the accuracy of the information on the form, sign and date it, retain a copy in the study file, and return a copy to Celgene or its representative.

3.1.1.6. Storage

At the study site, all investigational study drugs will be stored in a locked, safe area to prevent unauthorized access.

The study drug should be stored at room temperature away from direct sunlight and protected from excessive heat and cold.

3.1.1.7. Unused study drug supplies

Celgene will instruct the Investigator on the return or destruction of unused study drug. If any study drug is lost or damaged, its disposition should be documented in the source documents. Study drug supplies will be retained at the clinical site pending instructions for disposition by Celgene. Subjects will be instructed to return empty bottles or unused capsules.

3.1.1.8 Drug dispensing requirements

Pomalidomide (POMALYST®) will be provided to research subjects for the duration of their participation in this trial at no charge to them or their insurance providers. Pomalidomide will be provided in accordance with the Celgene Corporation's POMALYST REMSTM program. Per the standard POMALYST REMSTM program requirements, all physicians who prescribe pomalidomide for research subjects enrolled into this trial, and all research subjects enrolled into this trial, must be registered in and must comply with all requirements of the POMALYST REMSTM program.

Drug will be shipped on a per patient basis by the contract pharmacy to the clinic site for IND studies. Only enough pomalidomide for one cycle of therapy will be supplied to the patient each cycle. This is in accordance with the POMALYST REMSTM program.

3.2. Screening and Eligibility

The Investigator is responsible for keeping a record of all subjects who sign an Informed Consent Form for entry into the study. All subjects will be screened for eligibility. Screening procedures are outlined in Section 2, Schedule of Study Assessments and unless otherwise specified, must take place within 28 days prior to initiation of therapy.

3.3. Inclusion and Exclusion Criteria

Subjects are to be assessed for suitability for entry into the study based on the following inclusion and exclusion criteria.

3.3.1. Key Inclusion Criteria

Subjects must meet all of the following inclusion criteria to be eligible for enrollment into the study:

- Must be ≥ 18 years of age at the time of voluntarily signing an Institutional Review Board/Independent Ethics Committee (IRB/IEC) – approved informed consent form.
- 2. Must be diagnosed with myelofibrosis requiring therapy including myelofibrosis with myeloid metaplasia (MMM), de novo presentation (i.e. agnogenic myeloid metaplasia [AMMM], and developing after an antecedent history of Polycythemia vera (i.e., post-polycythemic myeloid metaplasia [PPMM]), or essential Polycythemia (i.e., post thrombocythemic myeloid metaplasia [PTMM]).
- 3. Screening total hemoglobin level < 10 g/dL or transfusion-dependent anemia defined as per IWG criteria (transfusion dependency defined by a history of a least 2 units of red blood cell transfusions in the last 28 days for hemoglobin < 8.5 g/dL that was not associated with overt bleeding).
- 4. Must have adequate organ function as demonstrated by the following \leq 14 days prior to starting study drug:
 - ALT (SGOT) and AST(SGPT) \leq 3 x upper limit of normal (ULN), [unless upon judgment of the treating physician, it is believed to be due to extramedullary hematopoiesis (EMH)]
 - Total bilirubin < 3 x ULN or Direct Bilirubin < 2 x ULN
 - Serum creatinine $\leq 2.5 \text{ mg/dL}$
 - Absolute neutrophil count $\geq 1,000/\mu L \ (\geq 1.0 \times 10^9/L)$
 - Platelet count $\geq 50,000/\mu L \ (\geq 50 \times 10^9/L)$
- 5. Subjects must be willing to receive transfusion of blood products.
- 6. ECOG performance status (PS) of 0, 1, or 2 at screening.
- 7. Must be willing to adhere to the study visit schedule and other protocol requirements.
- 8. No active malignancies with the exception of basal cell or squamous cell carcinoma of the skin, or carcinoma "in situ" of the cervix or breast.
- 9. All study participants must be registered into the mandatory POMALYST REMSTM program, and be willing and able to comply with the requirements of the POMALYST REMSTM program.
- 10. Females of reproductive potential (FCBP[†]) must adhere to the scheduled pregnancy testing as required in the POMALYST REMSTM program. Able to take

[†] A female of childbearing potential is a sexually mature woman who: 1) has not undergone a hysterectomy or bilateral oophorectomy; or 2) has not been naturally postmenopausal for at least 24 consecutive months (i.e., has had menses at any time in the preceding 24 consecutive months).

aspirin (81 or 325 mg) daily as prophylactic anticoagulation (patients intolerant to ASA may use warfarin or low molecular weight heparin).

3.3.2. Key Exclusion Criteria

- 1. Known positive status for HIV, hepatitis B carrier, or active hepatitis C infection.
- 2. The use of any growth factors, cytotoxic chemotherapeutic agents (e.g. hydroxyurea), corticosteroids, or experimental drug or therapy within 14 days of starting CC-4047 and/or lack of recovery from all toxicity from previous therapy to grade 1 or better.
- 3. Any serious medical condition or psychiatric illness that would prevent, (as judged by the treating physician) the subject from signing the informed consent form or any condition, including the presence of laboratory abnormalities, which places the subject at unacceptable risk if he/she were to participate in the study or confounds the ability to interpret data from the study.
- 4. Pregnant or lactating females.
- 5. Prior use of CC-4047.
- 6. Currently enrolled on another clinical trial or receiving investigational agent

3.4. Visit schedule and assessments

Screening Assessments and all on-study scheduled visits and assessments are outlined in Appendix M: Schedule of Assessments.

For females of child bearing potential, counseling about pregnancy precautions and the potential risks of fetal exposure must be conducted at a minimum of every 28 days. During counseling, subjects must be reminded to not share study drug and to not donate blood.

Pregnancy testing and counseling must be performed if a subject misses her period or if her pregnancy test or her menstrual bleeding is abnormal. Study drug treatment must be discontinued during this evaluation.

In addition to the required pregnancy testing, the Investigator must confirm with FCBP that she is continuing to use two reliable methods of birth control at each visit.

Counseling for all men about the requirement for latex condom use during sexual contact with females of childbearing potential and the potential risks of fetal exposure must be conducted at a minimum of every 28 days. During counseling, subjects must be reminded to not share study drug and to not donate blood, sperm, or semen.

An unscheduled visit can occur at any time during the study. Source documentation must be maintained for these unscheduled visits. The date for the visit and any data generated

must be recorded on the appropriate source. Source documents for these unscheduled visits must also be maintained.

At treatment discontinuation, subjects will undergo off study evaluations as outlined in Appendix M: Schedule of Assessments. In addition, a safety assessment will be done approximately 28 days post the last dose of study drug.

3.5. Drug Administration

3.5.1. Treatment

Subjects who meet entry criteria will be eligible to receive 0.5mg CC-4047 and prednisone.

3.5.2. Dosing regimen

Initial dosing of CC-4047 for eligible subjects will be 0.5mg daily. Subjects will receive oral CC-4047 from day 1 through day 28, continuously, in the absence of disease progression or toxicity warranting discontinuation of therapy. Twenty-eight days is considered one cycle of therapy. Dosing will be at approximately the same time each day. CC-4047 capsules should be swallowed whole, and should not be broken, chewed or opened. CC-4047 should be taken without food, at least 2 hours before or 2 hours after a meal. If a dose of CC-4047 is missed, it should be taken as soon as possible on the same day. If it is missed for the entire day, it should not be made up, rather it should be taken at the next scheduled time point. Patients who take more than the prescribed dose of CC-4047 should be instructed to seek emergency medical care if needed and contact study staff immediately.

Only one cycle of study drug will be supplied to the subject each cycle. Prednisone will be given during first 3 cycles of therapy. It will be dosed orally at the dose of 30 mg/day during cycle 1, 15 mg/day during cycle 2, and 15 mg every other day during cycle 3, and then it will be discontinued.

Subjects must also receive oral low-dose aspirin (81 mg) as prophylactic anti-thrombotic treatment unless it is contraindicated or the subject has a platelet count less than $75,000/\mu L$. If low-dose aspirin is contraindicated, the investigator should prescribe another appropriate prophylactic anti-thrombotic therapy.

Single oral CC-4047 doses of 1 and 50 mg in healthy adult males were safe and resulted in Cmax values of 11.2 and 288 ng/mL respectively. Given the short half-life in healthy adult male humans (approximately 8 to 11 hours) and once daily dosing, minimal accumulation is expected. A daily dosing schedule will be utilized for this study.

Subjects experiencing adverse events may need study treatment modifications (Table 1).

3.5.3. Special Handling Instructions

Females of childbearing potential should not handle or administer the clinical dosage forms unless they are wearing gloves.

3.5.4. Record of administration

Accurate recording of all study drug administration (including dispensing and dosing) will be made in the appropriate section of the source documents.

3.6. Dose Continuation, Modification and Interruption

All adverse events/toxicities are to be graded according to the Common Terminology Criteria for Adverse Events (CTCAE Version 3.0). Subjects who cannot tolerate dose of 0.5mg are to discontinue treatment. The dose of CC-4047 is not to be escalated.

3.6.1. CC-4047 Dose Reduction Steps

No reduction of the dose below 0.5mg a day is planned (Table 1).

3.6.2. Initiation of a New Cycle of Therapy

A new course of treatment may begin on the scheduled Day 1 of a new cycle if:

- The ANC is $\geq 1,000/\mu L (\geq 1 \times 10^9/L)$;
- The platelet count is $\geq 50,000/\mu L \ (\geq 50 \times 10^9/L)$;
- Any CC-4047-related allergic reaction/hypersensitivity or sinus bradycardia/ other cardiac arrhythmia adverse event that may have occurred has resolved to ≤ grade 1 severity;
- Any other CC-4047-related adverse event that may have occurred has resolved to ≤ grade 2 severity

If these conditions are not met on Day 1 of a new cycle, the subject will be evaluated weekly and a new cycle of CC-4047 will not be initiated until the toxicity has resolved as described above.

3.6.3. Instructions for dose modifications or interruption during a cycle.

Table 1: CC-4047 Dose Modification Guidelines

CTCAE CATEGORY	ADVERSE EVENTS	DOSING CHANGE
Allergy/Immunology	Allergic reaction/ hypersensitivity (including drug fever) Grade 2	Discontinue CC-4047.
	Allergic reaction/ hypersensitivity (including drug fever) Grade 3	Discontinue CC-4047.
Blood/ Bone Marrow	Neutropenia ANC < 500/μL (Grade 4) for >7 Days	Discontinue CC-4047.

CTCAE CATEGORY	ADVERSE EVENTS	DOSING CHANGE		
Blood/Bone Marrow	Thrombocytopenia Platelet count < 25,000/μL (Grade 4) for >7 Days	Discontinue CC-4047.		
Cardiovascular	Thrombosis/Embolism Grade 3 or 4	Hold CC-4047 and start systemic anticoagulation. Restart at the same dose level at investigator's discretion and only if approved by the Principal Investigator based on established significant benefit to the patient. The patient must sign consent form again to restart the therapy.		
Dermatology/Skin	Grade 3 Rash	Discontinue CC-4047.		
	Desquamating/Blistering Rash	Discontinue CC-4047.		
	Rash: Erythema multiforme	Discontinue CC-4047.		
Endocrine	Elevated or Reduced Thyroid Function Test results without symptoms of hyper- or hypo- thyroidism	Confirm test results. If significar refer for appropriate therapy. Maintain dose of CC-4047 if appropriate.		
	Elevated or Reduced Thyroid Function Test results with symptoms of hyper- or hypo- thyroidism	Hold study drug. Evaluate etiology and refer for appropriate therapy. Restart at the prior dose.		
Neurology	Neuropathy – Cranial/motor/sensory Grade 2	Hold CC-4047. Restart once adverse event is completely resolved.		
	Neuropathy – Cranial/motor/sensory Grade 3	Discontinue CC-4047.		
	Neuropathy – Cranial/motor/sensory Grade 4	Discontinue CC-4047.		
Other non-	Grade 3	Discontinue CC-4047.		
hematological, clinically significant toxicity	Grade 4	Discontinue CC-4047.		

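### Section 3.6.2 and Table 1 set different restart conditions for Grade 2 neuropathy, and 3.6.2 does not except the events for which Table 1 discontinues the drug

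*Combined protocol and SAP*

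**What the plan says.** Section 3.6.2 lists four conditions under which a new course may begin on the scheduled Day 1. Two are blood counts: neutrophils of at least 1,000/μL and platelets of at least 50,000/μL. The third is "Any CC-4047-related allergic reaction/hypersensitivity or sinus bradycardia/ other cardiac arrhythmia adverse event that may have occurred has resolved to ≤ grade 1 severity". The fourth is "Any other CC-4047-related adverse event that may have occurred has resolved to" Grade 2 or below. If they are not met, the subject is assessed weekly and "a new cycle of CC-4047 will not be initiated until the toxicity has resolved as described above".

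Section 3.6.3, by its heading, covers changes made within a cycle, and it consists of Table 1. Three of its entries matter here:

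- Grade 2 neuropathy (cranial, motor or sensory): "Hold CC-4047. Restart once adverse event is completely resolved".
- "Allergic reaction/ hypersensitivity (including drug fever) Grade 2", and the same reaction at Grade 3: discontinue.
- Other clinically significant non-hematological toxicity at Grade 3 or 4: discontinue.

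Section 3.6.2 does not mention Table 1, Table 1 does not mention 3.6.2, and no other section ranks them.

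**The concern.** Dosing is continuous, days 1 to 28 of 28-day cycles (section 3.5.2), and one cycle of drug is supplied at a time. Day 1 is therefore a real decision to dispense or not. A hold begun under Table 1 that is still in force on Day 1 comes under 3.6.2 as well, and for Grade 2 neuropathy the two give different conditions for resuming.

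At stake is whether a subject whom one page keeps off drug is dosed under another. Section 3.1 adds a practical risk. After at least 3 cycles without Grade 3 or 4 toxicity, monthly visits may move to a local referring doctor's office. Grade 2 neuropathy does not bar that move, so different clinicians may be applying different pages. Safety is a primary objective and endpoint (sections 2.1.1 and 2.2.1), so holds and restarts should follow one rule.

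**Working it through.** No arithmetic on the design applies, and the plan states no figure to reproduce. The check sets the two rules side by side for the same subject.

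**Step 1: do the two rules meet?** A hold that starts on day d of a 28-day cycle reaches the next scheduled Day 1 after 29 − d days: 28 days if d = 1, and 1 day if d = 28. Any hold lasting longer than 28 days must therefore cross a Day 1, and shorter ones may. This assumes that the cycle calendar keeps running during a hold. Section 3.1 supports that by requiring visits whether or not drug has been interrupted.

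**Step 2: Grade 2 neuropathy.** Assume that the event is judged related to CC-4047 and that both count conditions are met. Neuropathy is neither hypersensitivity nor arrhythmia, so the fourth condition of 3.6.2 applies (grade ≤ 2). Table 1 requires complete resolution.

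| Neuropathy on Day 1, after a Grade 2 hold | 3.6.2 (grade ≤ 2) | Table 1 (completely resolved) | Agree? |
|---|---|---|---|
| Grade 2, unchanged | 2 ≤ 2: may start | not resolved: stay on hold | No |
| Grade 1 | 1 ≤ 2: may start | not resolved: stay on hold | No |
| Fully resolved | may start | may restart | Yes |

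In the first row the subject meets 3.6.2 with no improvement at all.

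**Step 3: hypersensitivity.** The third condition of 3.6.2 (grade ≤ 1) restricts only reactions that reached Grade 2 or more. Table 1 discontinues at Grades 2 and 3. If discontinuation always comes first, this condition has almost no use for hypersensitivity, although it still serves arrhythmia.

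**Step 4: other related events.** The fourth condition of 3.6.2 (grade ≤ 2) restricts only events that reached Grade 3 or more. Table 1 discontinues at Grades 3 and 4 where the event is non-hematological and clinically significant. The overlap is therefore partial: hematological events fall outside that row, and Grade 3 or 4 thrombosis has its own hold-and-restart entry.

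**Step 5: is there a precedence rule?** None was found. The weekly-assessment sentence in 3.6.2 refers back only to its own thresholds.

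**The case against.** The strongest reply is that the sections act in order. Table 1 works within a cycle, and 3.6.2 works at the start of the next. Table 1 uses discontinue in contrast to hold, and section 3.6 says that subjects who cannot tolerate 0.5 mg stop treatment. On that reading a discontinued subject has no next cycle and never reaches 3.6.2. This stands as a reasonable reading of Steps 3 and 4, and what is left there is a missing exception and a nearly idle threshold. Section 3.4 does use the word discontinued for a temporary stop, but it limits that stop expressly to a pregnancy evaluation, so it says little about Table 1.

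The reply does not dispose of Grade 2 neuropathy. That row is a hold with a restart, so the subject does reach the next Day 1.

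Two further replies apply there. First, 3.6.2 is permissive, so a clinician could satisfy both passages by meeting both. Second, a specific row may be thought to override a catch-all condition. Either would settle the matter if the protocol said so, but it does not. Permission to dose on one page and an instruction to hold on the next still leave the decision to whichever page is read.

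A reader might go further and infer that three event classes carry flatly opposite instructions, or that every Grade 3 event is affected. The documents do not support either. The sequential reading is open for two of the classes, and the residual Table 1 row is limited to clinically significant non-hematological toxicity.

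**Conclusion.** The point holds in two parts of unequal strength. For Grade 2 neuropathy the restart conditions differ outright: a related event still at Grade 2 or at Grade 1 on Day 1, with adequate counts, passes 3.6.2 and fails Table 1. For hypersensitivity at Grades 2 and 3, and other clinically significant non-hematological toxicity at Grades 3 and 4, 3.6.2 fails to except events for which Table 1 discontinues. That is an ambiguity with a plausible resolution that the text leaves unstated.

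The consequence is for patient safety and uniform dosing. Frequency cannot be derived. The interim summary in the background section (addendum of 3/30/11) mentions one neutropenic fever and one DVT, in the same patient, among 20 evaluable subjects on the single agent. It gives no neuropathy rate and does not concern the prednisone combination.

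A reader might also infer a bias in the 6-cycle response rate. The documents do not show one. All eligible, consented subjects who began treatment are evaluable (section 5.2), and all who received any drug enter the safety analyses (section 5.4), so neither denominator depends on which restart rule is followed. Exposure of individual subjects could differ, but nothing allows an effect on response to be sized. The design figures are unaffected.

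**What to change.** Reconcile section 3.6.2 with Table 1 so that each event and grade carries one instruction. State which passage governs when Day 1 falls during or after a Table 1 event, and put a cross-reference in both places. For the discontinuation rows, say whether those subjects are outside 3.6.2. Check all Table 1 rows in the same pass. Which restart or stopping rule is intended is for the clinical team to decide, and this review takes no position on it.

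The cost is a protocol wording amendment with the usual IRB submission. It needs no extra subjects or procedures and no change to the sample size or decision rules.

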3.6.4. Treatment compliance

At all times, when dispensing study drug, research center personnel will review the instructions, printed on the packaging, with subjects. Subjects will be asked to maintain a diary to record the drug administration. Subjects will be asked to bring any unused study drug to the research center at their next visit. Research personnel will count and record the number of used and unused study drug capsules at each visit and reconcile with the subject diary.

3.7. Concomitant therapy

3.7.1. Recommended concomitant therapy

All supportive measures consistent with optimal subject care will be given throughout the study. Packed red blood cell transfusions are allowed when necessary. Growth factor use (including erythropoietin) is not allowed with the exception of the use of filgrastim (G-CSF) or pegfilgrastim, which is permitted when used to treat febrile neutropenia or those who have \geq grade 3 neutropenia and at the investigators discretion for prolonged neutropenia. Subjects should receive full supportive care, including transfusions of blood products, antibiotics and antiemetics and prophylactic treatment for potential hypersensitivity reactions and tumor lysis syndrome when appropriate. Splenic infarcts occasionally occur and should be managed with analgesics at the discretion of the clinician and do not necessarily require withdrawal from the study.

3.7.2. Anticoagulation Consideration

CC-4047 may increase the risk of thrombotic events in subjects who are at high risk or with a history a thrombosis, in particular when combined with other drugs known to cause thrombosis. When CC-4047 is combined with other agents such as steroids (e.g. dexamethasone, prednisone), anthracyclines (Doxil, adriamycin) and erythropoietin the risk of thrombosis may be increased.

Subjects must receive oral low-dose aspirin (81 mg) as prophylactic anti-thrombotic treatment unless it is contraindicated or the subject has a platelet count less than $75,000/\mu$ L. If low-dose aspirin is contraindicated, the investigator should prescribe another appropriate prophylactic anti-thrombotic therapy.

